Dexamethasone doses are those commonly used in neurooncology and there is an extensive experience in its use. It will be a short and descending course: 4mg/6 hours (2 days); 4 mg/8 hours (2 days); 2 mg/6 hours (2 days); 2 mg/8 hours (2 days); 1 mg/8 hours (2 days); 1 mg/12 hours (2 days).

Drug manufacture, blinding and supply of trial treatment

Dexamethasone (Forteocortin®) will be acquired from ERN, SA. Laboratories (Barcelona, Spain). The Son Espases Pharmacy Department will be in charge of developing and conditioning the 4mg, 2mg and 1mg dexamethasone / placebo capsules needed for 12 days of treatment, keeping the researchers blind.

The preparation and conditioning of the capsules will be carried out following the standardized work procedures of the pharmaceutical laboratory and its quality controls, previously authorized by the Agencia Española del Medicamento (AEMPS).

The Son Espases Pharmacy Department will be responsible for identifying the containers and sending them by courier to the participating hospitals. A record of the dispensing of test samples will be kept and will be sent in acknowledgment of receipt for control.

Patients, clinical staff, evaluators of the results as well as the statistical team that will perform the analysis will not know the assigned treatment. A randomization list will be created for each hospital. The randomization sequence will only be known by the Pharmacy Department of Son Espases Hospital.

Administration of trial treatment

Each patient will receive 3 containers with the correspondingly identified doses, and an information sheet explaining dose and frequency for proper oral administration.

Other treatments for traumatic brain injury

There is a wide spectrum of treatments for TBI. As the trial will be conducted in Spain, each participating site should follow its own clinical guidelines for the treatment of TBI patients. There is no need to withhold any clinically indicated treatment in this trial.

Dexamethasone or placebo would be provided as an additional treatment to the usual management of TBI.

Safety and Adverse events

Dexamethasone has a well documented safety profile. Nevertheless, data on adverse events, such as infectious complications, hyperglycemia, gastro intestinal bleeding or appearance of psychotic symptoms will be collected as secondary outcomes and will be presented to the independent Data Monitoring Committee (DMC) for blinded review.

Definitions

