The purpose of the sliding dichotomy approach is to increase the sensitivity (to lower the false negative rate) of the analysis. All these variables will also be analyzed in a pre-specified subgroup analysis comparing patients with a pericontusional edema volume of more than 10 mL in the pre-inclusion computed tomography (CT) scan in the study with those who have less than 10 mL of edema volume in the same CT study.

Interim analysis

Since the data available in this type of patients receiving this treatment are scarce and inconclusive as to the primary outcome variable, we will perform an interim analysis. A statistician ([name]) will blindly perform an interim analysis calculating the conditional power, an approach that quantifies the probability of obtaining a significant result at the end of the study given the data available after one year enrolling patients.

Since the probability chosen for futility in this trial is very small (< 0,15), it can be concluded that it would be useless to continue the trial. This interim analysis will be performed at the end of the first year since the inception of the trial, when it is estimated that about 100 patients will have been recruited. At the same time, a safety analysis will be also performed, focused on the adverse effects collected during the first year.

The results will be assessed and discussed by an independent Data Monitoring Committee, formed by one statistician and two experts in TBI, who will inform and make recommendations to the Trial Steering Committee, which will finally make the decisions.

Follow-up

No extra tests are required for the trial but a case report form should be completed at the end of the 12- day treatment, or at death or hospital discharge if either happens sooner. The GOSE and the neuropsychological evaluations will be performed one month and 6 months after the TBI. Both evaluations will be performed by clinical

neuropsychologists, and the protocol used will always follow the same process. The neuropsychological tests that will be performed are described in the Supplemental data

Sponsorship and trial management

This research project has no sponsor. The trial will be coordinated by the Trial Steering Committee (TSC).

Indemnity

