This project has been listed as a ``low intensity clinical trial'' by the Agencia Española del Medicamento (AEMPS). In this scenario, the damages on the patient that could result from taking part in this trial do not need to be covered by an specific insurance contract if they are covered by the individual or collective professional civil liability insurance or equivalent financial guarantee of the health trust where the clinical trial is carried out.

Protocol development

The Protocol Committee consists of the following investigators who are responsible for the development of, and agreeing to, the final protocol. Subsequent changes to the final protocol will require the agreement of the TSC.

Clinical experts: [name] [name], [name], [name] [name], [name] [name], [name] [name].

Statistician and Trial management: [name]

Independent Data Monitoring Committee (DMC)

[name] MD. Servicio de Neurocirugía. Hospital Universitario de Burgos. Spain.

[name] [name] [name]. Servicio de Medicina Intensiva. Hospital Virgen de la Salud. Toledo. Spain

[name] [name] MD; PhD. Servei de Salut de les Illes Balears, Palma de Mallorca, Spain, CRES/BSM Universitat Pompeu Fabra, Barcelona Spain.

To provide protection for study participants, an independent DMC has been appointed for this trial to oversee the safety monitoring. The DMC will review, after the first year, accumulating data from the ongoing trial and advise the TSC regarding the continuing

safety of current participants and those yet to be recruited, as well as reviewing the validity and scientific merit of the trial. The statistician ([name]) will provide (in a blind manner) the analysis service required by the DMC.

Standard operating procedures

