The DMC has the responsibility for making recommendations to the TSC, while randomization is in progress, to unblind the results. The DMC they will do this if, and only if, the following two conditions are satisfied: (1) the results provide proof beyond reasonable doubt that treatment is on balance either definitely harmful or definitely favourable for all, or for a particular category of participants in terms of the major outcome; and (2) the results, if revealed, would be expected to substantially change the prescribing patterns of clinicians who are already familiar with any other trial results that exist. Exact criteria for “proof beyond reasonable doubt” are not specified by a purely mathematical stopping rule, but they are strongly influenced by such rules.

Trial steering committee (TSC)

[name] [name]. Intensive Care Department. Son Espases Hospital. Palma de Mallorca.

[name]. Neurosurgery Department. 12 de Octubre Hospital. Madrid.

[name] [name]. Neurosurgery Department. 12 de Octubre Hospital. Madrid.

[name] [name]. Intensive Care Department. 12 de Octubre Hospital. Madrid.

[name] [name]. Neurosurgery Department. Son Espases Hospital. Palma de Mallorca.

[name]. Research Unit. Son Espases Hospital. Palma de Mallorca.

The role of the TSC is to provide overall supervision of the trial. In particular, the TSC will concentrate on the progress of the trial, adherence to the protocol, patient safety and consideration of new information. The TSC will take responsibility for: a) major decisions such as a need to change the protocol for any reason; b) monitoring and supervising the progress of the trial; c) reviewing relevant information from other sources; d) considering recommendations from the DMC.

When outcome data are available for the participants included during the first year, the TSC will review the rate of recruitment into the trial and the overall event rates. The TSC will consider the extent to which the rate of recruitment and the event rates correspond to those anticipated before the trial and will take whatever action is needed in light of this information.

Collaborators' responsibilities

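### The DMC may recommend unblinding only on proof of harm or benefit, yet the plan gives it blinded reports and no stated route to the arm codes

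*Combined protocol and SAP*

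**What the plan says.** All references are to the combined protocol and SAP.

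- **Safety and Adverse events:** data on infections, hyperglycaemia, gastrointestinal bleeding and psychotic symptoms "will be presented to the independent Data Monitoring Committee (DMC) for blinded review".
- **Interim analysis:** after one year a statistician "will blindly perform an interim analysis calculating the conditional power", with futility set at a conditional power below 0.15. The section adds: "At the same time, a safety analysis will be also performed, focused on the adverse effects collected during the first year". It continues: "The results will be assessed and discussed by an independent Data Monitoring Committee, formed by one statistician and two experts in TBI". The committee makes recommendations and the TSC decides.
- **Independent Data Monitoring Committee (DMC):** "The DMC will review, after the first year, accumulating data from the ongoing trial". The statistician "will provide (in a blind manner) the analysis service required by the DMC".
- **Randomization:** only the pharmacist knows the codes, until after the main analysis or until unmasking is needed. The Unblinding section describes a telephone route for clinicians, one patient at a time. Neither section names the DMC as someone who may ask for the key.
- **Standard operating procedures:** while randomization continues, the DMC may recommend unblinding to the TSC only if two conditions both hold. The first is proof beyond reasonable doubt that treatment is "definitely harmful or definitely favourable for all, or for a particular category of participants". The second is that disclosure would be expected to change prescribing substantially.
- **End of trial for participants:** the DMC may advise early termination. No evidential threshold is attached.

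**The concern.** The steps are in a circular order. To recommend unblinding, the DMC must already have concluded that dexamethasone is harmful or that it is favourable. To conclude either, it must know which arm received dexamethasone. The reports described to it are blind, and no route to the key is written for it.

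The DMC was set up to protect participants, and its first-year review informs the decision to expand from two hospitals to a network of 56. An imbalance in deaths, infections or good recovery would call for opposite advice depending on which arm it favoured. The futility analysis has the same difficulty: low conditional power for benefit and a strong trend towards benefit can come from the same coded table.

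**Working it through.** **1. The design figures reproduce, so they can be used for illustration.** Inputs from the sample size section are 50% against 62%, two-sided alpha 5%, power about 80% and 10% inflation. Allocation is 1:1 (Randomization). With mean proportion 0.56:

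n per arm = [1.96·√(2·0.56·0.44) + 0.8416·√(0.50·0.50 + 0.62·0.38)]² / 0.12² = 268, or 536 in total.

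536/0.9 = 596, against 600 stated. Power with 270 per arm (600 less 10%) is 80.4%. The sample size is not affected by this point.

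**2. What each reading of blind lets the DMC see.** The protocol does not define the word for the DMC.

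- Pooled data give one overall event rate and no comparison. For example, assumed adverse-event rates of 10% and 20% in equal arms appear as 15%.
- A/B-coded data give the size of a difference but not its sign.

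The first unblinding condition needs both size and sign, so it cannot be properly assessed under either reading.

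**3. What the sign does to the futility result.** Information fraction t = 100/600 = 0.167 (Interim analysis expects about 100 patients). The counts are assumptions chosen to mirror the design effect: 31/50 against 25/50.

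Z = (0.62 − 0.50)/√(0.56·0.44·2/50) = 0.12/0.0993 = 1.21.

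Conditional power for benefit, in the Brownian-motion approximation, is

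CP = 1 − Φ{[1.96 − Z√t − θ(1 − t)]/√(1 − t)},

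with θ = Z/√t for the current trend, or θ = 0.12/√(0.56·0.44·2/300) = 2.96 for the design effect.

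- If dexamethasone is better (current trend): [1.96 − 0.49 − 2.47]/0.913 = −1.10, so CP = 0.86.
- If placebo is better (current trend): [1.96 + 0.49 + 2.47]/0.913 = 5.39, so CP < 0.001.

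The second row below uses the minimum of 60 first-year patients given under Settings.

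| Look | Assumed counts | \|Z\| | Trend, dexamethasone better | Trend, placebo better | Design effect, dexamethasone better | Design effect, placebo better |
|---|---|---|---|---|---|---|
| 100 of 600 | 31/50, 25/50 | 1.21 | 0.86 | <0.001 | 0.86 | 0.51 |
| 60 of 600 | 19/30, 15/30 | 1.04 | 0.92 | <0.001 | 0.86 | 0.65 |

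Under the current trend, relabelling the same table moves the result across 0.15. Under the design effect it changes the value but leaves it above 0.15.

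**4. What a blind calculation can return.** The Interim analysis section defines conditional power as the chance of a significant final result, and alpha is two-sided. Without the key, a two-sided calculation under the current trend gives 0.86 whichever arm is dexamethasone. It would therefore support continuing even if dexamethasone were the worse arm.

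**The case against.** The strongest reply is that the protocol does not clearly blind the DMC. The lists of blinded parties name patients, clinical staff, evaluators and the statistical team, but not the DMC. Preparing an analysis blind describes how the statistician works. Only the wording in Safety and Adverse events refers to the committee's own review. Conditional power from observed data needs outcomes separated by arm, so coded arms are more plausible than pooled data. Coded arms would show the size of an imbalance, and the codes can be released when unmasking is required.

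Much of this stands, but it does not supply the sign. No passage gives the DMC the key or says it may request it, and the one rule on unblinding at its initiative demands proof first.

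The objection does rule out several stronger readings that a reader might infer:

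- *The DMC sees safety data only.* It also receives the interim conditional-power result and reviews accumulating data.
- *The DMC must have near-certain proof before acting on harm.* That test governs recommending unblinding. Advice on early termination, or on the continuing safety of participants, carries no such threshold.
- *The DMC can never tell harm from benefit.* The word blind is undefined and an unmasking provision exists, so the defect is a missing route, not a proven impossibility.
- *Using one standard for harm and benefit is itself an error.* It is a design choice. The criteria are not purely mathematical, so the text does not forbid more caution over harm.
- *The guidelines warn against the drug class.* The Background cites high-dose methylprednisolone and expressly distinguishes low-dose dexamethasone.

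**Conclusion.** The concern holds as an inconsistency between the DMC's directional test and the blind reporting described for it. As written, the committee would advise on safety, termination and expansion without knowing direction, and it could not properly assess the condition that permits unblinding.

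The size of the defect cannot be stated as a probability of missed harm, because no numerical rule exists. The illustration (0.86 against below 0.001) rests on assumed counts, on the normal approximation, and on projecting the current trend. The protocol's reference to the data available favours that projection but does not prescribe it. The share of patients enrolled after the look, (600 − 100)/600 = 83%, describes its timing and would be the same with an unblinded DMC, so it does not measure the defect.

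The conclusion also assumes that no separate DMC charter, outside this document, already gives the committee the key.

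**What to change.** - In Safety and Adverse events, Interim analysis and the DMC section, state that the DMC receives deaths, adverse events and one-month GOSE by arm, with the arm key sent to it directly and confidentially by Pharmacy.
- State that conditional power is evaluated in the direction of dexamethasone benefit. The blinded statistician can supply it under both labellings, and the DMC reads the relevant one with the key.
- State that the TSC, investigators, outcome assessors and report-preparing statistician stay blinded.
- In Standard operating procedures, reword the two-condition test so that it governs release of results to the TSC, not the DMC's own access to arm identity.

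The cost is protocol or charter wording and one code file. The committee already includes a statistician. The downside is that three independent members become unblinded. There is also a residual risk: a statistician who has seen both labelled values could infer the key from a decision to continue. Having the DMC's own statistician run that calculation would reduce it.

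A separate, lower evidence level for harm is optional and is not needed to resolve this point.

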-Number of episodes of neurological deterioration in both groups of patients during the 12 days of treatment.

- Symptoms associated with TBI in both groups of patients during the 12 days of treatment.
- Volume of pericontusional edema before and after 12 days of treatment in both groups of patients.
- Presence of adverse events between the two groups during the 12 days of treatment.
- Neuropsychological tests between the two groups of patients one month and 6 months after the TBI.

Estimated event rate

In our previous studies we have described that among TBI patients with brain contusions not treated with dexamethasone, the proportion of patients with good recovery (GOSE 7 and 8) was 50%.

Sample size and treatment effect size that should be detectable

Since the data available in this type of patients with this treatment is scarce and inconclusive, we will perform a randomized, triple-blind, placebo controlled trial with an interim futility analysis (interim analysis). The primary endpoint for the DEXCON TBI trial is the good recovery (GOSE 7-8) one month after the TBI.

A study with 600 patients would have about 80% power (two sided alpha=5%) to detect a 12% absolute increased (from 50% to 62%) in good recovery (GOSE 7-8). It includes an inflation of 10% due to non-adherence (withdrawal of consent, loss to follow-up, cross-over or change of treatment).

Recruitment of collaborating investigators

The trial will recruit hospitals from Spain. Suitable collaborating hospitals and investigators will be assessed in terms of the trauma service that they provide and their ability to conduct the trial.

Before the trial can begin at any site, the local Principal Investigator must agree to adhere to Good Clinical Practice Guidelines and all relevant national regulations. In addition, all relevant regulatory and ethics approvals should be in place before the trial starts at a site.

Ethical considerations, information giving and written informed consent

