Adverse events (AE): Any undesirable and unintended medical occurrence affecting a trial participant during the course of a clinical trial.

Serious adverse events (SAE): A serious adverse event (experience) is any undesirable medical occurrence that results in death or is life-threatening or requires inpatient hospitalization or prolongation of existing hospitalization, or results in persistent or significant disability/incapacity.

Reporting of adverse events for this trial

Death, life-threatening complications, and prolonged hospital stay which is attributable to the adverse event are pre-specified outcomes to be reported in this trial. This clinical trial is being conducted in an emergency condition using a drug in common use. It is important to consider the natural history of the critical medical event affecting each patient enrolled, the expected complications of this event, and the relevance of the complications to dexamethasone.

Adverse events to be reported using an adverse event reporting form will be limited to those trial outcomes that might occur and be reasonably attributable to the trial drug. Events that are part of the natural history of the primary event of TBI or expected complications of TBI should not be reported as adverse events.

If an SAE occurs, a written report must be submitted within 24 h. The Trial Steering Committee (TSC) will coordinate the reporting of all SAEs to all relevant Regulatory Agencies, Ethics Committees and local investigators as per local legal requirements.

Unblinding

In general there should be no need to unblind the allocated treatment. Unblinding should be done only in those rare cases when the clinician believes that clinical management depends importantly upon knowledge of whether the patient received dexamethasone or placebo. In those few cases when urgent unblinding is considered necessary, a 24-h telephone service will be available. The caller will be told whether the patient received dexamethasone or placebo.

Data collection and management

This trial will be coordinated from Son Espases Hospital. Data will be collected at each site by local investigators and sent to the TSC. These data will be collected from the patient's routine medical records and no special tests will be required.

All data on adverse events, including those routinely collected as outcomes, will be collected and reported as required by the relevant authorities.

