This procedure will be performed again centrally in the 12 de Octubre hospital, Madrid. Previously, the patient's data will be anonymized and the images will be sent through a web platform with a secure server for review. In a central way, the total volume of the contusion will be established as well as the volume of the edema by means of a semi-automatic method using the Analyze software (vesion 10.0; Analyze Direct, Stilwell, Kansas, USA) of which a license is available. The method consists of a semi-automatic analysis in which in each axial section a central voxel is selected and thanks to the density selection, voxels with similar density characteristics are selected.

The performance of measurements in each hospital and subsequent centralization of the images will allow to establish the interobserver and intermethod reproducibility of the measurement of the edema associated with the contusions, in addition to estimating in two ways the difference of measurements at two time points throughout the study and after an intervention.

-Compare the presence of adverse events between the two groups during the 12 days of treatment.

Those adverse effects that have special interest and serious adverse effects will be collected. Side effects of special interest are:

-Metabolic: Hyperglycemia will be especially monitored. The maximum value of capillary glycemia will be recorded daily. The amount of daily insulin that the patient needs to control de glucose level will also be collected.

-Psychiatric: presence of psychotic symptoms using the Confusion Assessment Method (CAM).

-Digestive: Episodes of gastro intestinal hemorrhage; Episodes of epigastric pain, vomiting or reflux symptoms.

-Infectious: Presence of new infectious episodes. Infectious episode will be confirmed in accordance with the Centers for Disease Control (CDC) criteria and mainly based on microbiological criteria.

- Compare the results of the neuropsychological tests between the two groups of patients one month and 6 months after the TBI.

Two neuropsychological evaluations will be performed: 1 month and 6 months after the TBI. Both evaluations will be performed by clinical neuropsychologists, and the protocol to be used will always follow the same procedure and tests. The tests that integrate this protocol are described below:

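### The adverse-event reporting rule conflicts with the plan's own safety outcomes, and nothing says which rule prevails or which data source feeds the safety comparisons

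*Combined protocol and SAP*

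**What the plan says.** Under Reporting of adverse events for this trial, the protocol sets two filters. Entries on the adverse event form are "limited to those trial outcomes that might occur and be reasonably attributable to the trial drug". In addition, events belonging to the natural course of the injury are excluded, and "expected complications of TBI should not be reported as adverse events". The same section requires a written report within 24 h of any serious adverse event (SAE).

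Other parts of the document set no such conditions:

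- Definitions describes an adverse event as "Any undesirable and unintended medical occurrence affecting a trial participant during the course of a clinical trial".
- Secondary outcomes lists "Presence of adverse events between the two groups during the 12 days of treatment".
- Safety and Adverse events names adverse events that include "infectious complications, hyperglycemia, gastro intestinal bleeding or appearance of psychotic symptoms will be collected as secondary outcomes", and sends them to the Data Monitoring Committee (DMC) for blinded review.
- Supplemental data 1 says how these are ascertained. For infection the item is "Presence of new infectious episodes", confirmed by CDC criteria. It also collects serious adverse effects.
- Data collection and management says that all adverse event data, including data gathered as outcomes, are collected and reported as the authorities require.
- Monitoring says that the DMC reviews adverse events that could in theory be linked with the product and with the condition studied.
- Interim analysis plans a safety analysis of the adverse effects gathered in the first year.

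**The concern.** Pneumonia after a brain injury shows the difficulty. A site may regard it as an expected complication, in which case the reporting section says it is not an adverse event to report. It is also a new infectious episode, which Supplemental data 1 says is counted and compared between arms. Both instructions are in force and they give different answers.

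The filters are also poorly suited to a randomised, blinded comparison. A clinician who does not know the allocation cannot reliably tell a drug-related infection from a background one in a single patient. A causal excess shows when all events are counted and the arms compared. Setting events aside by individual judgement lowers the counts on which that comparison rests.

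At stake are the between-arm adverse-event outcome and the year-one safety analysis that goes to the DMC. The problem would grow if recruitment moves from two hospitals to the 56-hospital network, since each site would have to settle the conflict for itself.

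**Working it through.** **Setting the rules side by side.** The question for each class of event is whether the text gives one answer.

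1. *The four named harms (infection, hyperglycaemia, gastrointestinal bleeding, psychotic symptoms).* Safety and Adverse events and Supplemental data 1 collect them with no test of cause: daily maximum capillary glucose and daily insulin, the Confusion Assessment Method, bleeding episodes, and infections confirmed mainly on microbiology. The reporting section would exclude any of them judged expected after the injury. Collection as an outcome is clear. Whether the event also counts as an adverse event, and which record is analysed, is not.
2. *SAEs.* The 24 h rule has no exemption, and Supplemental data 1 collects serious adverse effects. The exclusion of expected complications has no exemption for serious events either. The two are not reconciled.
3. *Death.* It is a pre-specified outcome to be reported and also enters the GOSE, so it is better protected.
4. *Non-serious events outside the special-interest list.* Their only stated route is the filtered form.
5. *Data source.* Neither Analysis, Interim analysis nor Supplemental data 1 says whether the safety comparison uses the adverse event form or the outcome case report form (CRF).

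**What filtering would do if it operated.** The documents give no adverse event rates and no share of events set aside, so every rate below is an assumption. The planned 600 patients, allocated 1:1, give 300 per arm. As a check on the method, the plan's own sample size reproduces: 50% v 62%, two-sided 5%, 80% power gives 268 per arm, 536 in total, and 536/0.9 = 596 against the stated 600.

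The formula, with p̄ the mean of the two rates, is

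power = Φ{ [|p1 − p0| − 1.96·√(2p̄(1 − p̄)/n)] / √[(p0(1 − p0) + p1(1 − p1))/n] }.

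For 20% v 30% and n = 300: (0.10 − 1.96 × 0.03536)/0.03512 = 0.874, so power is 81%. If half the events in each arm are kept, 10% v 15% is observed: (0.05 − 1.96 × 0.02700)/0.02693 = −0.109, so power is 46%.

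| Assumed true rates | All kept | 75% kept | 50% kept | 25% kept |
|---|---|---|---|---|
| 10% v 18% | 81% | 67% | 48% | 27% |
| 20% v 30% | 81% | 65% | 46% | 24% |
| 30% v 40% | 73% | 55% | 36% | 19% |

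With 270 per arm (10% loss), the 20% v 30% row becomes 77%, 61%, 42% and 22%.

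The risk ratio does not move: 30/20 = 15/10 = 1.5. Filtering that is equal in both arms shrinks the absolute difference (from 10 points to 5 when half are kept) and the power, but not the relative effect. Since each hospital has its own randomisation list in blocks of two, a site's habit falls on nearly equal numbers in each arm. Variation between sites therefore lowers counts without in itself favouring an arm.

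**The case against.** The strongest reply is that the filter governs a form and not outcome collection. The attribution sentence concerns the adverse event form, and the exclusion sentence stands under a heading about reporting. The steroid harms have a separate stream with objective ascertainment, and the DMC receives it. Monitoring extends DMC review to events linked with the condition. SAEs are to be reported within 24 h and death is a named outcome. On this reading the protocol already does most of what is wanted.

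Much of this stands. A reader might infer that the rule hides a dexamethasone excess in infection, hyperglycaemia, bleeding or psychosis. The documents do not support that, because all four are collected with no attribution test. Nor do they support the inference that the DMC sees only filtered data, or that filtering would differ by arm.

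The reply does not settle the matter, for three reasons. The exclusion sentence does not mention the form: it says such events are not to be reported as adverse events, the same term used for the secondary outcome. The attribution sentence refers to trial outcomes directly. And no sentence names the record from which the safety comparisons are drawn. The two-stream reading is reasonable, but the text does not secure it.

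**Conclusion.** This is an internal inconsistency that should be corrected. It is not a demonstrated bias. The reporting rule conflicts with the protocol's own adverse event definition, with the statement that all adverse event data are collected, with the between-arm outcome, with the section naming the four harms, and with Monitoring. The exposure is to SAEs and listed events that a site regards as expected after brain injury, which can be handled differently by site and under-counted, and to the final and interim safety analyses if they draw on the form. Non-serious events outside the list are exposed as well.

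The size cannot be estimated from the documents. The power losses above are illustrative, rest on assumed rates and assumed equal filtering in both arms, and apply only to events that actually pass through the filter. They should not be read as the expected loss for infection, which has its own route. The plan's sample size is unaffected.

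**What to change.** Amend the reporting section and Supplemental data 1 to state that:

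- all special-interest events listed in Supplemental data 1, all SAEs and all deaths are recorded and compared by arm, regardless of attribution or expectedness;
- the outcome CRF holding these records is the source for the final between-arm safety comparison and for the interim safety analysis given to the DMC;
- the attribution and expectedness filter applies only to decisions on expedited regulatory reporting.

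The same amendment should say whether non-serious events outside the list belong to the between-arm adverse-event outcome, since Supplemental data 1 suggests that they do not and the main text does not say. Attribution can still be recorded as a descriptive field.

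The cost is protocol wording, CRF guidance to sites, and somewhat more entries. The burden should be small because the main event types are already listed for collection.
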